3.3 Randomization

A randomized double-blind design has been chosen in order to ensure a balanced allocation of study subjects to the treatment arms and to minimize bias in therapeutic management and in outcomes assessment.

Randomization and treatment assignments will be performed via Interactive Response Technology (IRT) prepared on behalf of the Sponsor (under the responsibility of the Data Science (DS) Department of APEB). Specific procedures for randomization through the IRS are contained in the study procedures manual.

A total of 450-600 planned subjects will be randomized to receive one of the 2 treatment arms in a 2:1 ratio as follows:

- Roxadustat (planned 300-400 subjects)
- Placebo (planned 150-200 subjects)

Randomization will be stratified by the following four factors:

- Region (region A versus region B)*
* assignment to region (see Section 6.5.2) will be determined based on health care system comparability.
- Screening Hb values (≤ 8.0 g/dL versus > 8.0 g/dL)
- History of cardiovascular, cerebrovascular or thromboembolic diseases (Yes versus No).
- eGFR (< 30 mL/min/1.73 m² versus ≥ 30 mL/min/1.73 m²).

Subjects randomized to roxadustat QW, BIW or TIW prior to implementation of protocol v2.0 will be pooled together. Subjects randomized to placebo will also be pooled together.

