7.5.1.2 Proportion of subjects with TEAEs by SOC/PT

The number and percentage of subjects with TEAEs, as classified by SOC and PT will be summarized by treatment arm. Summaries will be provided for:

- TEAEs
- TEAEs (by PT only)
- Drug related TEAEs,
- TEAEs with NCI CTC Grade 3 or higher
- TEAEs by severity

- Drug related TEAEs by severity
- Serious TEAEs,
- Drug related serious TEAEs,
- TEAEs leading to permanent discontinuation of study drug,
- Drug related TEAEs leading to permanent discontinuation of study drug,
- TEAEs excluding serious adverse events that equal to or exceed a threshold of 5.0% in any treatment arm (roxadustat or placebo),
- TEAEs leading to death,
- Drug-related TEAEs leading to death,
- Common TEAEs that equal to or exceed a threshold of 5.0% in any treatment arm (roxadustat or placebo)
- TEAEs by relationship to the study drug,
- AEs occurring during the post study follow up period
- Serious AEs during the post-study follow up period
- Onset of common ($\geq 5\%$ in Any treatment arm(roxadustat or placebo)) TEAEs by treatment duration: <3 months, ≥ 3 to ≤ 6 months, >6 to ≤ 12 months, >12 months

For the summaries by severity or relationship to the study drug, in the subject count, if a subject has multiple TEAEs with the same SOC or PT, but with different severity or relationship, then the subject will be counted only once with the worst severity and highest degree of relationship, however, if any of the severity or relationship values are missing then the subject will be counted only once with missing severity or relationship. In the adverse event count, the adverse events will be presented in each category they were classified to. Drug related TEAEs will be presented in a similar way by severity only.

Maximum severity or relationship will be defined as the worst severity and highest degree of relationship on-treatment (see Section 6.2).

No queries will be done for SMQs.

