7.5.1.3 Event-rates per 100 patient-years

The number of events and event rate (per 100 patient years) during the Safety Emergent Period with TEAEs, as classified by SOC and PT will be calculated by treatment arm. Summaries will be provided for:

- TEAEs
- TEAEs censored at start of chronic dialysis
- TEAE NCI CTC Grades 3 or higher
- Serious TEAEs,
- TEAEs leading to death.

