7.5.1.4 Incidence rates and cumulative incidence

Since the percentage of adverse events might be different between treatment arms due to the difference in the discontinuation rates, in addition to the frequency tables above, the incidence rate (per 100 subject years at risk) and the cumulative incidence at 6 months, 12,

18 months & 24 months with the 95% confidence interval, using Greenwood's formula, will be reported by treatment arm.

It will be done for each of the following event types of special interest:

- Serious TEAEs,
- TEAE for each SOC (>10% for a SOC in total SAF)
- Deaths occurring during the Safety Emergent Period,
- Any death (including post-study follow up period),
- Related serious TEAEs,
- AEs leading to discontinuation of study drug, and
- TEAE NCI CTC Grades 3 or higher.

Hazard ratios of each of the TEAE categories of special interest above will be computed by using Cox Proportional Hazards regression stratified on region and history of CV and adjusted on baseline Hb and baseline eGFR as continuous covariates. Hazard ratios (roxadustat as relative to placebo) and their 95% CI will be calculated for each TEAE category.

As a sensitivity analysis, the above analysis will be repeated using IPCW method (Appendix 10.7) for the following event types of special interest:

- Serious TEAEs,
- TEAE for each SOC (>10% for a SOC in total SAF)
- Deaths occurring during the Safety Emergent Period, and
- TEAE NCI CTC Grades 3 or higher.

A dot-and-forest plot will be produced showing each of the above TEAE categories on the y-axis. The incidence rates by treatment arm, the stratified Cox hazard ratios (roxadustat as relative to placebo) and their 95% CI will be shown on the x-axis.

In addition, cumulative incidence plots for subjects experiencing each of the TEAE categories above will be produced by treatment arm.

Incidence rate (per 100 subject years at risk) in each treatment arm by SOC and PT and the cumulative incidences by SOC will also be produced for the most common TEAEs ($\geq 5\%$ in total SAF). In addition, cumulative incidence plots of subjects experiencing at least one most common TEAEs in a SOC will be produced. A dot-and-forest plot will be produced showing each SOC in the y-axis and the incidence rates, the Cox hazard ratio and its 95% CI in the x-axis. The SOC will be sorted by the hazard ratio.

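### SAP 7.5.1.4 picks adverse events for time-at-risk analysis by their pooled frequency, while 7.5.1.2 uses frequency in either arm; with 2:1 allocation some one-sided events miss those outputs

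*SAP*

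**What the plan says.** SAP 7.5.1.2 lists, among the frequency tables, "Common TEAEs that equal to or exceed a threshold of 5.0% in any treatment arm (roxadustat or placebo"). It applies the same either-arm rule to the non-serious TEAE table and to the table of onset by treatment duration.

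SAP 7.5.1.4 uses a different base, the total safety analysis set (SAF), in two places:

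- Incidence rates by SOC and PT and cumulative incidences by SOC are planned for the "most common TEAEs ($\geq 5\%$ in total SAF"). These feed plots of subjects with at least one such event in a SOC, and a summary plot: "A dot-and-forest plot will be produced showing each SOC in the y-axis and the incidence rates, the Cox hazard ratio" and its confidence interval.
- The event types that get an incidence rate, cumulative incidence, a Cox hazard ratio and an IPCW repeat include "TEAE for each SOC (>10% for a SOC in total SAF").

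SAP 7.5.1.5 repeats the 7.5.1.4 analyses with censoring at chronic dialysis, again for the most common PTs. It sets no threshold of its own, so it inherits the pooled one.

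SAP 7.5.1.3 has no frequency threshold. It gives numbers of events and event rates per 100 patient-years "with TEAEs, as classified by SOC and PT will be calculated by treatment arm".

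The SAP gives no reason for using two rules. Protocol 7.5.1 plans cumulative incidence and incidence rates for TEAEs without a frequency threshold.

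**The concern.** A threshold on the pooled percentage works against events that differ between arms, because the low arm dilutes the high one. Those are the events for which a between-arm safety comparison is most useful. SAP 7.5.1.4 justifies its analyses by saying that crude percentages may mislead when the arms discontinue at different rates. Yet its entry rule is a crude percentage taken over those same two arms.

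What is at stake is limited to which PTs get a first-event, time-at-risk incidence rate and feed the SOC-level common-TEAE displays, and which SOCs get a hazard ratio and an IPCW repeat as event types. No hypothesis test, alpha allocation or efficacy endpoint depends on it.

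**Working it through.** The plan states no figure that depends on this threshold, so there is nothing to reproduce first.

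**Inputs.** From SAP 3.3: "Roxadustat (planned 300-400 subjects") and "Placebo (planned 150-200 subjects"), which is 2:1. The thresholds are those in SAP 7.5.1.2 and 7.5.1.4. I take the SAF to equal the planned randomized numbers. The percentage limits below need only the 2:1 ratio.

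**Formula.** With R the percentage on roxadustat and P the percentage on placebo:

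pooled % = (2R + P) / 3

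A PT fails the 5% pooled rule when 2R + P < 15. A SOC fails the >10% pooled rule when 2R + P ≤ 30.

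**Limits for a PT.**

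| Rate in the other arm | Roxadustat excess missed if below | Placebo excess missed if below |
|---|---|---|
| 0% | 15/2 = 7.5% | 15% |
| 2% | (15 − 2)/2 = 6.5% | 15 − 4 = 11% |
| 4% | (15 − 4)/2 = 5.5% | 15 − 8 = 7% |

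**Counts needed to enter.**

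| Planned size | Pooled rule | Either-arm rule |
|---|---|---|
| 300:150 | 23 of 450 | 15 of 300 or 8 of 150 |
| 400:200 | 30 of 600 | 20 of 400 or 10 of 200 |

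**Examples that meet the either-arm rule and fail the pooled rule.**

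| Roxadustat | Placebo | Pooled | Fisher exact p |
|---|---|---|---|
| 20/300 (6.7%) | 2/150 (1.3%) | 22/450 = 4.9% | 0.011 |
| 22/300 (7.3%) | 0/150 | 22/450 = 4.9% | 0.0001 |
| 26/400 (6.5%) | 3/200 (1.5%) | 29/600 = 4.8% | 0.0075 |
| 0/300 | 22/150 (14.7%) | 22/450 = 4.9% | <0.0001 |

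**How often the rules disagree.** This is the exact binomial probability that a PT reaches 5% in an arm but not pooled, for assumed true rates.

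| True rates, roxadustat v placebo | 300:150 | 400:200 |
|---|---|---|
| 6% v 2% | 45% | 45% |
| 8% v 3% | 10.4% | 6.5% |
| 10% v 2% | 2.2% | 0.8% |
| 2% v 8% | 78% | 84% |

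**SOC rule.** At 11% v 6% the pooled figure is (22 + 6)/3 = 9.3%, so the SOC is not selected. With no cases in the other arm, a SOC at up to 15% on roxadustat or 30% on placebo is not selected.

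**Does the either-arm rule lose anything?** The pooled percentage is a weighted mean of R and P, so at least one arm is at or above it. Every PT or SOC that passes the pooled rule therefore passes the either-arm rule. Enumerating all PT counts at both sizes found no exception.

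**The case against.** A reader might infer that the missed events get no exposure-adjusted comparison at all. The documents do not support that. SAP 7.5.1.3 gives event rates per 100 patient-years by PT and arm for all TEAEs, and again with censoring at chronic dialysis. A reader might also infer that PT-level hazard ratios are lost. None is planned at any frequency. A PT below the cut-off still counts in its SOC's hazard ratio when that SOC passes 10%, and in the serious, related serious, grade 3 or higher and discontinuation hazard ratios where it meets those definitions. SAP 7.5.1.2 also tabulates every TEAE by PT and arm.

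It can further be said that the affected band is narrow for a roxadustat excess, the direction of most safety interest. The 45% disagreement belongs to rates beside the cut-off and fades quickly above it. A shorter list for extra displays is also a legitimate choice.

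Most of this stands, and it is why the point is minor. Three things remain. The 7.5.1.3 rates come with no planned confidence interval, cumulative incidence or hazard ratio. Their denominator in SAP 6.2.1.6 divides summed exposure days by the Safety Emergent Period in years, which as written does not give patient-years. That is a separate matter, but it weakens the fallback. And a wish for a shorter list does not explain why the base changes from either arm to pooled.

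**Conclusion.** The inconsistency is real and its effect is minor. A PT at 5% or more in one arm but below 5% pooled keeps its event rate per 100 patient-years. It has no time-at-risk incidence rate and does not enter the SOC-level common-TEAE cumulative incidence or hazard-ratio plot. The band reaches just under 7.5% for a roxadustat-only event and just under 15% for a placebo-only event, and it shrinks as the other arm's rate rises. So the larger gap concerns events less frequent on roxadustat.

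A SOC above 10% in one arm but not pooled gets no hazard ratio as an event type and no IPCW repeat. It could still appear in the common-TEAE plot if one of its PTs passes the 5% rule, but that hazard ratio would cover only the common PTs.

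The limits rest on 2:1 allocation holding in the SAF. The counts and p values also assume that the SAF equals the planned numbers. The rates used for the disagreement probabilities are illustrative and do not come from the documents.

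**What to change.** In SAP 7.5.1.4, replace *≥5% in total SAF* with *≥5.0% in any treatment arm (roxadustat or placebo)*. Replace *>10% for a SOC in total SAF* with *>10% for a SOC in any treatment arm*, in both the hazard-ratio list and the IPCW list. State in 7.5.1.5 that the most common PTs are chosen by the same rule. If the pooled base is intended, give the reason instead.

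The cost is the two threshold phrases, one clause in 7.5.1.5, and a few more rows in existing tables and plots.

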7.5.1.5 Sensitivity/Subgroup analyses

- Subgroups of interest :

The number and percentage of subjects reporting TEAEs in each treatment arm will be tabulated by SOC and PT for the subgroups of interest defined in Section 7.8

- Baseline eGFR category (< 15 vs ≥ 15) only :

The following summaries will be provided by comparing Baseline eGFR categories (< 15 vs ≥ 15) :

- Event rate per 100 patient-years for TEAEs by SOC and PT
 - Incidence rate and cumulative incidence for serious TEAEs
 - Incidence rate and cumulative incidence for deaths during the safety emergent period
 - Incidence rate and cumulative incidence for drug-related serious TEAEs
 - Incidence rate and cumulative incidence for AEs leading to discontinuation of study drug
 - Incidence rate and cumulative incidence for TEAE NCI CTC Grades 3 or higher
- Incidence rate and cumulative incidence censoring events occurring on or after the start of chronic dialysis :

The same analysis in incidence as described in Section 7.5.1.4 will be performed (i.e., incidence rate, hazard ratios, dot-and-forest plots and cumulative incidence plots) by censoring all data occurring at initiation of chronic dialysis (see Section 6.2.1.3 for more details regarding the definition of time to event and time to censoring) :

It will be done for :

- Serious TEAEs
- Serious TEAEs by baseline eGFR category (< 15 vs ≥ 15)
- Deaths occurring during the Safety Emergent Period,
- Deaths occurring during the Safety Emergent Period by eGFR category (< 15 vs ≥ 15)
- Drug-related serious TEAEs,
- Drug-related serious TEAEs by eGFR category (< 15 vs ≥ 15)
- AEs leading to discontinuation of study drug,
- AEs leading to discontinuation of study drug by eGFR category (< 15 vs ≥ 15)
- TEAE NCI CTC Grades 3 or higher
- TEAE NCI CTC Grades 3 or higher by eGFR category (< 15 vs ≥ 15)
- Incidence rate for TEAE by SOC and most common PTs
- Cumulative incidence by SOC for most common PTs.

7.5.1.6 AEs within 7 days

Additional summaries or analyses with events to be considered restricted to any adverse event starting up to Analysis Date of Last Dose + 7 days:

- Overview summary table of subjects with AEs
- Number and percentage of subjects with AEs, as classified by SOC and PT
- Number and percentage of subjects with AEs leading to death, as classified by PT
- Incidence rate for serious AEs (i.e., incidence rate, hazard ratios, dot-and-forest plots and cumulative incidence plots as described in Section 7.5.1.4 will be provided)
- Incidence rate for AEs NCI CTC Grades 3 or higher (i.e., incidence rate, hazard ratios, dot-and-forest plots and cumulative incidence plots as described in Section 7.5.1.4 will be provided)

Pre-specified adjudicated cardiovascular and thrombo-embolic events will be analyzed in meta-analyses across multiple phase 3 studies and compared between treatment groups (roxadustat versus control). The statistical method for this analysis pooling studies will be detailed in a Pooled Statistical Analysis Plan (pSAP). The results will be presented in a separate report.

All data will also be listed. All Adverse Events collected from site 70051 will be listed separately.

7.5.2 Clinical Laboratory Evaluation

Descriptive statistics for laboratory values (in SI units) and changes from baseline at each assessment time point and for the maximum and minimum on-treatment (i.e., during Safety Emergent Period) value will be presented by treatment arm and treatment for the quantitative laboratory parameters.

Maximum and minimum on-treatment values will be determined using all the original values and not the derived windows.

Shift tables and number and percentage of subjects with shift to low and shift to high will be reported by treatment arm for the quantitative laboratory parameters.

Box plots of quantitative laboratory values (in SI units) versus visit will be produced by treatment arm (two arms in one page).

A plot for each parameter of mean (+/- 95% CI) versus visit will be produced by treatment arm (two arms in one page).

Summary by visit for qualitative laboratory parameters will be provided by treatment arm.

All clinical laboratory data will also be listed.

Potentially clinically significant (PCS) laboratory abnormalities

For each potentially clinically significant (PCS) criterion defined in Section [6.2.3.1](#) the percentage of subjects with abnormalities by visit and at any moment during the Safety Emergent Period and who did not meet the criteria at baseline will be reported by treatment arm.

Incidence rate (per 100 subject years at risk) and the cumulative incidence at 6 months, 12, 18 months & 24 months with the 95% confidence interval using Greenwood's formula of PCS abnormalities will also be reported, using only subjects who did not meet the criteria at baseline, by treatment arm. Risk of PCS abnormalities will be compared using the same Cox model as used in Section [7.5.1](#) Hazard ratio and its 95% will be calculated for the frequency of roxadustat as relative to placebo. A dot-and-forest plot will be produced showing the PCS abnormalities above in the y-axis and the incidence rates, the Cox hazard ratio and their 95% CI in the x-axis.

In addition, cumulative incidence plots for subjects experiencing each PCS abnormality will be produced by treatment arm (two arms in one page).

7.5.2.1 Liver function tests

Descriptive summary of PCS values in Liver Enzymes and Total Bilirubin will be provided as per Astellas standard TLB_005 and FFG_008.

In addition, a matrix scatter plot of Liver Enzymes and Bilirubin (as in Astellas standard FFG_009) will be plotted showing the maximum ALT, AST, ALP and total bilirubin during the Safety Emergent Period crossed against each other. Different dots will be used for roxadustat and placebo.

Individual displays of Liver Enzymes and Bilirubin parameters, listed in Section [6.2.3.1](#) will be reported for all subjects with ALT and / or AST > 3 x ULN or total bilirubin > 2 x ULN during Safety Emergent Period.

For subjects who require further liver function investigations, additional information will be collected and listed.

7.5.3 Vital Signs

Descriptive and changes from baseline for vital signs (systolic blood pressure, diastolic blood pressure, respiratory rate, weight and pulse) at each assessment time point and for the maximum and minimum on-treatment (i.e during Safety Emergent Period) value will be presented by treatment arm.

Maximum on-treatment value will be determined using all the original values and not the derived windows.

A plot for each parameter of mean (+/- 95% CI) versus visit will be produced by treatment arm (two arms in one page).

PCS Vital signs criteria (10 Combined) will be analyzed in the same way as explained in Section [7.5.2](#) for PCS laboratory abnormalities.

All vital signs data will also be listed.

7.5.4 Electrocardiograms (ECGs)

Descriptive and changes from baseline for ECG parameters (Pulse, PR Interval, RR Interval, QRS interval, QT interval, and QTc interval) at each assessment time point and for the maximum on-treatment (i.e during Safety Emergent Period) value will be presented by treatment arm.

Maximum on-treatment value will be determined using all the original values and not the derived windows.

The number and percentage of subjects with post-baseline PCS values (see [Table 8](#)) will be tabulated by treatment group. The percentages are to be calculated relative to the number of subjects with available baseline and at least one post-baseline assessment. The numerator will be total number of subjects with at least one post-baseline PCS ECG value. Shift tables may be presented.

The following PCS QTc Criteria (both QTcB and QTcF) :

- QTc > 500 msec
- Change from baseline in QTc > 60 msec

will be analyzed separately in the same way as explained in Section 7.5.2 for PCS laboratory abnormalities.

A plot for each parameter of mean (+/- 95% CI) versus visit will be produced by treatment arm (two arms in one page).

In addition, ECG parameters will be reported according to Astellas standards TEG_003 and TEG_004.

All ECG data will also be listed.

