6.2.4 Physical Examination

A comprehensive physical examination will be conducted during the screening period and at the EOT visit and recorded in the source documents. This examination will include general appearance and the following body regions and systems: head, eyes, ears, neck and throat (HEENT), lungs, heart, chest and back, abdomen, genitourinary, extremities, skin and any other, if deemed necessary.

A targeted examination (e.g., respiratory and cardiovascular) will be conducted and recorded in the source documents.

Only the date of the physical examination will be recorded in the eCRF. There will be no table or listing for the physical examination. Any clinically relevant adverse change will be recorded as an AE in the eCRF.

6.2.5 12-lead Electrocardiogram (ECG)

The 12-lead ECG measurements will be performed on all subjects at specific times. A single ECG measurement will be taken with the subject in the supine position, after the subject has been lying quietly for 5 minutes. Clinically significant abnormalities will be reported as an AE.

The visit, ECG date, Pulse, RR Interval, PR interval, QRS Interval, QT Interval, overall interpretation and relevant comments will be recorded in the eCRF.

Baseline assessment is the assessment from day 1 visit. If day 1 assessment is missing, screening period assessment will be used in the analysis.

QTc interval will be calculated using both

- Bazett ($QTcB = QT/(RR \text{ Interval})^{1/2}$) and
- Fridericia ($QTcF = QT/(RR \text{ Interval})^{1/3}$) corrections,

where QT is in msec and RR Interval in seconds; and if RR Interval is not available, it will be replaced with 60/HR.

For all ECG parameters, the maximum post-baseline value on treatment will be defined (see Section 6.2).

ECG values are potentially clinically significant (PCS) if they meet or exceed the upper limit values listed in Table 8 below.

Table 8 ECG Parameters classification

ECG Parameter	Classification
QTc interval (msec)	> 450 msec, > 480 msec, > 500 msec;
QTc interval change (msec)	> 30 msec and > 60 msec (increase from baseline)
QRS (msec)	≥ 150 msec
PR (msec)	≥ 250 msec

Time to occurrence of PCS ECG :

For the two QTc criteria ($QTc > 500$ msec ; change from baseline in $QTc > 60$ msec), the time to occurrence (in years) for a subject with occurrence of the PCS at any moment during Safety Emergent Period (defined in Section 6.2) will be calculated (in years) as defined in Section 6.2.2

Time to censoring will be defined as :

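### The SAP's ECG outlier table counts subjects already abnormal at baseline, which dilutes the arm comparison for QTc >450, QTc >480, QRS ≥150 and PR ≥250 msec

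*SAP*

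**What the plan says.** SAP 6.2.5, Table 8, sets the ECG criteria. The absolute QTc limits are "> 450 msec, > 480 msec, > 500 msec". The other absolute limits are QRS ≥150 msec and PR ≥250 msec. Table 8 also has two relative criteria, QTc increases of more than 30 and more than 60 msec.

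SAP 7.5.4 then specifies the count table. Numerator: "The numerator will be total number of subjects with at least one post-baseline PCS ECG value". Denominator: "The percentages are to be calculated relative to the number of subjects with available baseline and at least one post-baseline assessment". Baseline status plays no part in either. On displays that would separate old from new abnormality, the section says only "Shift tables may be presented".

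Still in 7.5.4, two criteria (QTc >500 msec and QTc change >60 msec, each for Bazett and Fridericia) "will be analyzed separately in the same way as explained in Section 7.5.2 for PCS laboratory abnormalities".

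SAP 7.5.2 handles laboratory PCS values differently. The percentage covers subjects with an abnormality "and who did not meet the criteria at baseline will be reported by treatment arm", and incidence rates and cumulative incidence are computed "using only subjects who did not meet the criteria at baseline, by treatment arm". SAP 7.5.3 sends the vital-sign PCS criteria to the same method, and Table 6 already builds a change from baseline into each of them.

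Protocol 7.5.4 says PCS ECG values will be reported with statistics like those used for treatment-emergent adverse events. Protocol 7.5.1 defines such events as new, or worse in severity, after the first dose.

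**The concern.** Of the three safety domains with PCS criteria, ECG is the only one whose main count mixes pre-existing and new abnormality. The SAP gives no reason for this. A subject with a QRS of 155 msec before the first dose and again at week 12 is a case in the table, although nothing has emerged on treatment.

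Such subjects are possible here. No exclusion criterion in protocol 3.2 names QTc, QRS or PR, and history of cardiovascular, cerebrovascular or thromboembolic disease is common enough to be a stratification factor.

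Two things are at stake for the four unprotected criteria. Pre-existing cases are added to both arms, which moves the ratio towards 1; in a safety table that is the unreassuring direction in which to err. And any chance difference between the arms in baseline abnormality passes into the tabulated comparison.

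**Working it through.** **Which criteria are affected.** Setting Table 8 against SAP 7.5.4:

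| Criterion | Can be met at baseline? | Required analysis that excludes baseline cases |
|---|---|---|
| QTc >450, QTc >480 msec | Yes | None |
| QTc >500 msec | Yes | Yes, under 7.5.2 |
| QTc change >30 msec | No | Not needed |
| QTc change >60 msec | No | Not needed, but given under 7.5.2 |
| QRS ≥150 msec | Yes | None |
| PR ≥250 msec | Yes | None |

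Four criteria are left: QTc >450, QTc >480, QRS and PR.

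**Size of the dilution.** The documents give no figure for this table, so there is none to reproduce. What follows is illustration under assumed rates.

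Inputs:
- 150 placebo and 300 roxadustat subjects, the minimum planned (SAP 3.3 and 4).
- Two-sided 0.05 (SAP 7.1), used only as a yardstick, since the count table specifies no test.
- Assumed: new-onset risk r of 5% on placebo and 15% on roxadustat among baseline-normal subjects; persistence p of 90%; baseline prevalence b from 0 to 40%.

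Formulas:
- Rate shown by the table = b·p + (1 − b)·r.
- Difference shown = (1 − b)(0.15 − 0.05).
- Power = Φ[(|difference| − 1.96·SE₀)/SE₁], with SE₀ pooled and SE₁ unpooled. Under the baseline-normal rule both arms shrink by the factor (1 − b).

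Example at b = 20%: placebo 0.18 + 0.80 × 0.05 = 22.0%; roxadustat 0.18 + 0.80 × 0.15 = 30.0%; ratio 30.0/22.0 = 1.36.

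| b | Shown: placebo vs roxadustat | Difference (points) | Ratio shown | Power, table rule | Power, baseline-normal rule (ratio 3.0) |
|---|---|---|---|---|---|
| 0% | 5.0% vs 15.0% | 10.0 | 3.00 | 91% | 91% |
| 2% | 6.7% vs 16.5% | 9.8 | 2.46 | 86% | 91% |
| 5% | 9.2% vs 18.8% | 9.5 | 2.03 | 77% | 90% |
| 10% | 13.5% vs 22.5% | 9.0 | 1.67 | 63% | 88% |
| 20% | 22.0% vs 30.0% | 8.0 | 1.36 | 43% | 84% |
| 40% | 39.0% vs 45.0% | 6.0 | 1.15 | 23% | 70% |

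A second set of assumptions gives the same pattern. With new onset of 6% versus 12% (true ratio 2.0) and full persistence, b of 10%, 20% and 30% gives 15.4% vs 20.8% (1.35), 24.8% vs 29.6% (1.19) and 34.2% vs 38.4% (1.12).

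**Chance imbalance.** The standard error of the between-arm difference in baseline prevalence is √[b(1 − b)(1/300 + 1/150)] = 0.1·√[b(1 − b)]. That is 1.4 points at b = 2%, 3.0 at 10% and 4.0 at 20%. A baseline difference of d points moves the rate difference shown by about d·(p − r), here 0.75d to 0.85d. At b = 20%, one standard error therefore moves it by 3.0 to 3.4 points, against an expected 8.0. This can go either way. It is sampling noise that the power column already includes, and it is not a bias.

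**The case against.** The strongest reply is that the QTc criteria of most weight are already handled. QTc >500 msec and QTc change >60 msec get baseline-filtered percentages, incidence rates, Cox hazard ratios and cumulative incidence. That stands, and it is why the point is limited to four criteria.

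Other information also remains. SAP 7.5.4 summarises changes from baseline for PR, QRS, QT and QTc at each time point and for the on-treatment maximum, and clinically significant ECG abnormalities are reported as adverse events. This stands in part: distributions of change would show a general shift, but they do not count new threshold crossings.

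The SAP revision history (version 2.0, item 10) records a deliberate choice to focus on QTc. That entry concerns time-to-event analysis, not the count table. The protocol (1.2.2) reports a thorough QT study in healthy subjects without QT prolongation, which lowers the prior concern for QTc.

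SAP 7.5.4 also cites sponsor standards TEG_003 and TEG_004, which are not in the documents. They may contain baseline-by-post-baseline displays; this cannot be checked.

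A reader might infer that a treatment-emergent QTc, QRS or PR signal would be swamped. The documents do not support that. They give no baseline prevalence; the loss is small at about 2%. Randomisation balances pre-existing cases on average, so the expected direction is not reversed. The absolute difference also holds up better than the ratio: 8.0 of 10.0 points remain at b = 20%.

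**Conclusion.** The point holds as a narrow inconsistency. For QTc >450, QTc >480, QRS ≥150 and PR ≥250 msec, the SAP requires no count confined to subjects who were free of the abnormality at baseline, whereas it does so for laboratory values and vital signs. The required table shows post-baseline prevalence for these criteria, and the between-arm ratio is diluted.

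How much is unknown. In the illustration the loss is minor at about 2% baseline prevalence (ratio 3.0 shown as 2.46, power 86% instead of 91%) and substantial at about 20% or more (ratio 1.36, power 43% instead of 84%). Those figures rest on assumed prevalence, persistence and new-onset rates. The primary and key secondary efficacy analyses are untouched. This is a low-priority improvement worth making because it is so cheap.

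**What to change.** Add to SAP 7.5.4: for QTc >450, QTc >480, QRS ≥150 and PR ≥250 msec, report by arm the number and percentage of subjects with at least one post-baseline value meeting the criterion, among those with a baseline ECG not meeting it and at least one post-baseline ECG. This applies the 7.5.2 baseline rule and states the numerator and denominator together. Keep the present count as a supplementary line, and change the baseline-by-worst-post-baseline shift tables from optional to mandatory for these criteria.

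The cost is a sentence or two and a filter already specified for laboratory values; no new data are needed. The denominator becomes slightly smaller, by the share of subjects abnormal at baseline. In the illustration the baseline-normal rule still has 84% power at 20% prevalence, so the gain from removing pre-existing cases outweighs that loss.
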